6.3 Missing Data Imputation

Missing Data Imputation for SVR

HCV RNA values will be selected for analysis based on the analysis windows defined in Section 6.2.

For analyses of SVR, subjects' missing visit values will have backward imputation applied, if possible. For backward imputation, if the nearest HCV RNA value after the SVR window is unquantifiable or undetectable, then it will be used to impute the HCV RNA value in the SVR window. If a subject is missing an HCV RNA value within the appropriate SVR window after performing backward imputation, then this value will be imputed with an HCV RNA value from a local laboratory if present; otherwise, the HCV RNA value will be missing. Subjects with missing HCV RNA data in the analysis window, after imputations, will be imputed as a failure.

Regardless of the imputation method described above, if a subject starts another treatment for HCV, then all HCV RNA values for this subject measured on or after the start date of the new HCV treatment will be excluded from analyses. The subject will be considered a failure for summaries of viral response at all time points after the start of the new HCV treatment.

Missing Data Imputation for Virologic Failure

If HCV RNA values from the central laboratory are missing but a local laboratory value is present in the appropriate time period, then the local laboratory value will be used to assess post-treatment relapse and on-treatment virologic failure.

Missing Data Imputation for PRO Questionnaires

The handling of missing data for patient reported outcomes (PROs) will be as follows. If a respondent answers at least 50% of the items in a multi-item scale of the PedsQL, the missing items will be imputed with the average score of the answered items in the same scale. In cases where the respondent did not answer at least 50% of the items, the score for that dimension will be considered missing.

Regardless of the imputation method described above, if a subject starts another treatment for HCV, then all PRO data for this subject measured on or after the start date of the new HCV treatment will be excluded from analyses.

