All subjects who receive at least one dose of study drugs who fail to achieve virologic suppression, or who experience virologic breakthrough on DAA therapy will be discontinued from treatment and enter the Post-Treatment Period, unless alternative management is agreed to with Primary Therapeutic Area Medical Director. The investigator can prescribe another regimen, as deemed appropriate, which will not be provided or reimbursed by AbbVie.

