### **8.1.2.3 Additional Efficacy Endpoints**

1. The percentage of subjects with HCV RNA < LLOQ at each post-baseline visit in the Treatment Period (using data as observed);
2. The percentage of subjects with SVR4 by age group and overall;
3. The percentage of subjects with SVR24 by age group and overall;
4. The percentage of subjects who relapsed after achieving SVR12 by age group and overall;
5. Change from baseline to all post-baseline visits in Fibrotest score and APRI by age group and overall.

All rates will be presented with 2-sided 95% confidence intervals using the Wilson's score method.

In addition, a summary of reason for SVR24 non-response (e.g., on-treatment virologic failure, relapse, reinfection, other) will be provided for each age group.

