**Post Treatment Period**

Activity	PT Wk 4	PT Wk 12	PT Wk 24	PT Wk 36	PT Wk 48	PT Wk 96	PT Wk 144	Premature D/C
Vital Signs, Weight, Height, Body Mass Index	X	X	X	X	X	X	X	X
Urine Pregnancy Test a	X							X a
Longitudinal Fibrotest and APRI		X			X	X	X	X
Hematology/Chemistry/Urinalysis b /Coagulation Panel b	X	X			X	X	X	X
HCC Assessment: Liver Ultrasound c			X			X	X	X
HCC Assessment: Alpha fetoprotein c			X		X	X	X	X
Concomitant Medication Assessment d	X	X	X	X	X	X	X	X
Adverse Event Assessment e	X	X	X	X	X	X	X	X
HCV RNA Samples	X	X	X	X	X	X	X	X
HCV Resistance Sample f	X	X	X	X	X	X	X	X
Patient Reported Outcome g		X						X g
HIV RNA Samples h	X	X						
Flow Cytometry h	X							

D/C = Discontinuation

- a. A positive urine pregnancy test requires a confirmatory serum test. (Refer to Section 5.3.1.1 [Pregnancy Test] for additional details.) Females who are experiencing menses or are nearing sexual maturation in the opinion of the PI or who are of childbearing potential should have urine pregnancy testing done through Post-Treatment Week 4. Pregnancy testing will be performed at PT Premature D/C visit only if the subject discontinues prior to PT Wk 4.
- b. Urinalysis will not be conducted after the Post-Treatment Week 4 visit. Urinalysis will be performed at PT Premature D/C visit only if the subject discontinues prior to PT Wk 4. The coagulation panel will be obtained at PTW4 for all patients. For non-cirrhotic subjects: Perform the coagulation panel at visits only if clinically indicated after post treatment Week 4.
- c. HCC assessment for subjects with compensated cirrhosis only.

- d. Concomitant medication will be collected for 30 days after study drug has been stopped, thereafter only antiviral medicines taken for the treatment of HCV and medications taken for SAEs will be recorded. See section 5.2.3.
- e. Non-serious AEs and all SAEs will be collected until 30 days post dosing. Only spontaneously reported SAEs will be collected thereafter. See Section 6.1.
- f. Resistance samples are only collected for patients that meet virologic failure criteria and should be drawn at the confirmatory visit, and if confirmed, at all subsequent visits.
- g. The PRO should be administered as the first study procedure. PRO will be accessed at the Premature D/C visit only if the subject discontinues prior to PT Wk 12.

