Analysis 3: Analysis 3 will be applicable to Cohort 1 only. In subjects with or without baseline polymorphisms in NS3 only, in NS5A only, any in NS3, any in NS5A, any in NS3 or NS5A, and any in NS3 + NS5A at the *key subset of amino acid positions* at 15% detection threshold, the SVR₁₂ rate will be calculated, and the rates with or without polymorphisms will be compared using Fisher's exact test. Analysis will be separated by HCV subtype. The following tables will be provided (mITT-VF):

- Comparison of SVR₁₂ rates by subtype, and total (including all subtypes)
- Comparison of SVR₁₂ rates by genotype, and total (including all genotypes)

Analysis 4:

The following analyses will be performed for subjects who do not achieve SVR₁₂ (with separate summaries for subjects in PVF and non-PVF populations) and have post-baseline resistance data available:

- Listings by subject of all *treatment-emergent variants* relative to the baseline amino acid sequences will be provided for each DAA target (NS3/4A and NS5A).
- Listings by subject of all *variants at signature amino acid positions* in a post-baseline time point for each DAA target (NS3 and NS5A).
- The persistence of post-baseline variants at signature resistance-associated amino acid positions for each target (NS3 and NS5A) from subjects will be assessed at Post-Treatment Week 24. Listings by subject and time point of all treatment-emergent variants will be provided for each DAA target (NS3 and NS5A).

HCV Genotype/Subtype

Phylogenetic analysis will be conducted on HCV sequence from baseline samples for all subjects in Part 1, and from subjects with available sample in Part 2 in order to accurately determine subtype.

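### SAP 6.3 sets aside HCV RNA and PRO data once another HCV treatment starts, but has no such rule for FibroTest/APRI or resistance sequences

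*SAP*

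**What the plan says.** SAP 6.3 has two rules triggered by the start of another HCV treatment. For virology, "then all HCV RNA values for this subject measured on or after the start date of the new HCV treatment will be excluded from analyses", and the child's response status is then fixed: "The subject will be considered a failure for summaries of viral response at all time points after the start of the new HCV treatment". For questionnaires, PRO data "measured on or after the start date of the new HCV treatment will be excluded from analyses". SAP 10.10 repeats the PRO rule. Neither document has a third rule.

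Other parts of the plan make such data possible:

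- Protocol 5.5.1, on children who fail to suppress or who break through: "The investigator can prescribe another regimen, as deemed appropriate". Protocol 5.4.1.1 keeps children with virologic failure in follow-up for resistance until 144 weeks post-treatment.
- Protocol Appendix C, Post Treatment Period, note f: resistance samples "should be drawn at the confirmatory visit, and if confirmed, at all subsequent visits".
- SAP 10.8.1 calls a variant treatment-emergent if it is new since baseline or has risen by at least 20 percentage points. Nothing in the definition depends on which therapy the child was taking.
- Protocol 8.1.2.3 lists as an additional efficacy endpoint: "Change from baseline to all post-baseline visits in Fibrotest score and APRI by age group and overall". SAP Table 10 gives these measures post-treatment windows up to Study Drug End Day 1,999. SAP 11.3.1 and 11.3.2 place them among the chemistry variables summarised as mean change at each post-baseline visit, including post-treatment visits.

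**The concern.** The SAP accepts that a measurement taken after a second HCV regimen no longer describes GLE/PIB, and it acts on this for HCV RNA and PROs. FibroTest, APRI and viral sequence can also be changed by a second regimen. A child cured by another regimen may show improving fibrosis markers, and that improvement would be averaged into the GLE/PIB change from baseline. A child still viraemic on or after another regimen may carry variants which that regimen selected. Under the SAP's definition those variants would be listed as treatment-emergent or persistent.

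Emergence and persistence of variants is a secondary objective (protocol 4.2), and it is studied in the children most likely to be re-treated. Very few failures are expected, so a misread profile would not be diluted by many others.

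**Working it through.** There is no planned figure to reproduce. The check compares the rules and then sizes the gap.

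**Which outputs have a cut-off at new HCV treatment**

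- HCV RNA and viral response: yes (SAP 6.3).
- PedsQL: yes (SAP 6.3 and 10.10).
- FibroTest and APRI: no. The only timing condition in SAP Table 10, beyond the windows themselves, is Study Drug End Day above 2.
- Resistance sequences: none stated (SAP 10.8.1; protocol 8.1.6.1).

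**Routes by which a sequence after re-treatment can enter**

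1. The sample at 24 weeks post-treatment. It is analysed only if variants were already found at failure or discontinuation. The SAP assesses persistence at Post-Treatment Week 24, while protocol 8.1.6.1 says through Week 144, which would lengthen the exposure.
2. A failure with HCV RNA below 1000 IU/mL, where the first later sample reaching 1000 IU/mL is used, with no upper time limit.
3. The non-PVF group in SAP 10.8.1 (SVR12 non-responders without virologic failure), sequenced at a time point of at least 1000 IU/mL after discontinuation, again with no upper limit.

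All three need a child who has been re-treated and still has at least 1000 IU/mL.

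**How many children are at risk**, assuming adult rates apply to the planned 125 (protocol 8.2)

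The adult figures are from protocol section 3.0. There were 23 virologic failures, of which one was a re-infection, leaving 22. SVR12 was reached by 2206 of 2256, leaving 2256 − 2206 = 50 non-responders. The expected number is 125 × p, and P(at least one) = 1 − (1 − p)^125.

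- Virologic failure: p = 22/2256 = 0.98%; 125 × p = 1.2; P = 0.71.
- Any SVR12 non-response: p = 50/2256 = 2.2%; 125 × p = 2.8; P = 0.94.

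The documents do not give the share re-treated, so these are upper counts.

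**How many sequences might be affected**

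As pure assumptions, take 25% to 75% re-treated before Week 24, and 5% to 20% of those with at least 1000 IU/mL afterwards.

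- Low end: 1.2 × 0.25 × 0.05 = 0.015 children.
- High end, from virologic failures: 1.2 × 0.75 × 0.20 = 0.18.
- High end, from all non-responders: 2.8 × 0.75 × 0.20 = 0.42.

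**Weight of one re-treated child in a FibroTest/APRI mean**, which is 1/n with complete data

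- Overall: 1/125 = 0.8%.
- Part 2 age group, from 81/3 = 27 children: 1/27 = 3.7%.
- Part 2 age group at the 22 per group on the final dose (protocol 5.5.3): 1/22 = 4.5%.
- Part 1: 1/44 = 2.3%.

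The shift in the mean is this weight times the part of that child's change due to the second regimen. The documents give no size for that change.

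**The case against.** The strongest reply is that the resistance outputs are largely protected by design, and much of this stands. Protocol 5.4.1 wants the discontinuation visit within 2 days of the last dose and before any other anti-HCV therapy. Resistance samples are drawn at the confirmatory visit, and the SAP uses the first qualifying sample after failure, so the failure sample will usually predate a second regimen. An effective second regimen leaves little virus to sequence. The outputs for failures are by-subject listings, not pooled estimates. Post-treatment HCV medications are captured and summarised (SAP 7.3), so a careful reader could trace a re-treated child.

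It can also be argued that excluding HCV RNA values from analyses removes the value that qualifies a sample for sequencing. That reading is possible, but the SAP does not state it. The rule sits under SVR imputation, and the SAP needed a separate sentence for PROs.

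For FibroTest and APRI, SAP 10.7 does not carry them as efficacy endpoints, and keeping all observed laboratory data in a descriptive summary is defensible. The protocol does name their change from baseline as an efficacy endpoint, however, and the SAP does not say that the retention is deliberate. The same silence covers other laboratory, vital-sign and growth data, which are not put forward as efficacy measures.

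A reader might infer that the resistance conclusions are broadly contaminated, or that one child could make up 20% to 100% of the paediatric resistance data. The documents do not support that. Such a share assumes 1 to 5 failures and that the rare event has already happened. Nor does any text expressly attribute these later data to GLE/PIB. The attribution follows from a single treatment with no cut-off and no flag.

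**Conclusion.** The gap is real and modest. As written, FibroTest and APRI values after a second HCV regimen enter the GLE/PIB change-from-baseline summaries, at about 0.8% of the overall mean and about 4% of a Part 2 age-group mean per re-treated child. For resistance the exposure is confined to the three routes above. At adult rates 1 to 3 of 125 children would be at risk, and most likely none or one would have an affected sequence.

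This rests on adult failure rates carrying over to children and on an unknown re-treatment share. AUC, SVR12 and the Fisher comparisons of baseline polymorphisms are not affected. It is worth correcting because the SAP already applies the principle elsewhere and the remedy is cheap, not because a main conclusion is in danger.

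**What to change.** Extend SAP 6.3 so that resistance sequences, FibroTest and APRI collected on or after the recorded start of another HCV treatment are left out of the GLE/PIB treatment-emergent, persistence and change-from-baseline outputs. List those data separately by subject, with the new regimen and its start date. In SAP 10.8.1, state that the rule applies to the failure sample, the Week 24 sample and the non-PVF samples. Reconcile the persistence horizon (Week 24 in the SAP, Week 144 in the protocol) at the same time.

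This is one added rule and one listing. Protocol 5.2.3 already has HCV antivirals recorded throughout follow-up, so no new data collection and no change to patient care is needed. The cost is a few fewer late observations in the main outputs, and the listing keeps them visible.

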7.0 Demographics, Baseline Characteristics, Medical History, and Other Medications

The ITT population will be used to summarize demographics, baseline characteristics, medical history and previous, concomitant, and post-treatment medications; data will be summarized across all subjects and by age group.

7.1 Demographic and Baseline Characteristics

Categorical demographic and baseline characteristic variables will be summarized with the number and percentage of subjects. Continuous variables will be summarized with descriptive statistics (number of non-missing observations, mean, standard deviation, median, maximum and minimum).

Continuous demographic variables include age, weight, height, and body mass index (BMI), BMI z score (BMI z score will be calculated using WHO published BMI-for-age z score tables),⁵ weight and height z scores (weight and height z scores will be calculated using WHO published weight-for-age z score and height-for-age z score tables).

Categorical demographic variables include sex, race, black race (black or non-black), ethnicity, age category (≥ 3 to < 6 years, ≥ 6 to < 9 years, ≥ 9 to < 12 years, ≥ 12 to < 18 years), birth year, weight category (≥ 12 to < 20 kg, ≥ 20 to < 30 kg, ≥ 30 to < 45 kg, ≥ 45 kg), weight z score category (< -1 , -1 to 1 , > 1), Height z-score category (< -1 , -1 to 1 , > 1), BMI z-score category (< -1 , -1 to 1 , > 1) country, and geographic region (North America, Europe, or Japan).

Weight-for-age reference data are not available beyond age 10 because this indicator does not distinguish between height and body mass in an age period where many children are experiencing the pubertal growth spurt and may appear as having excess weight (by weight-for-age) when in fact they are just tall. Subjects who are older than 10 years at the time of the corresponding weight measurement will be excluded from the summary of weight z score.

When defining geographic region, sites in the United States, Puerto Rico, and Canada will be grouped under North America; sites in Belgium, Germany, Russia, Spain and the United Kingdom will be grouped under Europe; sites in Japan will be grouped together as Japan.

Continuous baseline characteristics include baseline \log_{10} HCV RNA level, creatinine clearance, eGFR, platelet count, albumin, GGT, alpha fetoprotein (for cirrhotic subjects only), Fibrotest, APRI, FIB-4, AST, ALT, total, direct, and indirect bilirubin for all subjects.

Categorical baseline characteristics include:

- HCV genotype and subtype (using central laboratory results and final genotype/subtype results, see Section 10.8);
- Prior HCV treatment history (naïve or experienced);
- For treatment-experienced subjects, type of previous regimen (IFN- or SOF-based);
- For treatment-experienced subjects, type of non-response to previous treatment (on-treatment nonresponder or breakthrough, post-treatment relapse, or unknown/other);
- Baseline fibrosis stage (equivalent to Metavir F0 – F1, F2, F3, or F4);
- Baseline cirrhosis status (cirrhotic or non-cirrhotic)
- Baseline HCV RNA level ($< 1,000,000 \geq 1,000,000$ to $< 2,000,000, \geq 2,000,000$ IU/mL);
- Baseline platelet count (< 90 or $\geq 90 \times 10^9/L$);
- Baseline albumin (< 35 or ≥ 35 g/L);
- Baseline eGFR ($< 30, \geq 30$ to $< 60, \geq 60$ to $< 90, \geq 90$ mL/min/1.73 m²);
- HIV co-infected subjects (yes/no);
- History of bleeding disorders (yes/no);
- History of depression or bipolar disorder (yes/no);
- Injection drug use (yes, within last 12 months; yes, more than 12 months ago; or no);

- Subject on stable opiate substitution (yes/no);
- Nicotine use (user, ex-user, or non-user);
- Alcohol use (drinker, ex-drinker, or non-drinker);
- Concomitant use of Proton Pump Inhibitors (PPIs).
- Concomitant use of Statins (yes/no);

In addition, for cirrhotic subjects, the following will be summarized:

- Baseline Child-Pugh score (5, 6, or > 6),
- Baseline alpha fetoprotein (< 20 or \geq 20 ng/mL),

For treatment experienced subjects, any regimen that contains SOF with or without IFN or RBV is SOF-based. Otherwise, any regimen that contains IFN with or without RBV is IFN-based.

Any concomitant medication coded to the WHO Drug Dictionary ATC code of A02BC will be counted as a PPI. Any concomitant medication coded to the WHO Drug Dictionary ATC code of C10AA or C10BX will be counted as a statin.

Baseline fibrosis stage is defined for subjects with non-missing liver biopsy scores, FibroScan scores, or FibroTest scores. Only one score will be used to categorize each subject even if a subject has more than one score recorded. If a biopsy score is present, then it will be used to categorize the subject, regardless of the FibroScan/FibroTest score. Similarly, if a FibroScan score is present along with a FibroTest score, then the FibroScan score will be used to categorize the subject. If biopsy and FibroScan scores are not present and more than one FibroTest result is available, then the baseline FibroTest result (i.e., last non-missing FibroTest result on or before Day 1) will be used to categorize the subject. Subjects will be categorized as F0 – F1, F2, F3, or F4 according to [Table 11](#).

Table 11. Baseline Fibrosis Stage

Baseline Fibrosis Stage, Metavir Equivalents	Liver Biopsy Metavir, Batts Ludwig, Knodell, IASL, Scheuer, New Inuyama or Laennec Score	Liver Biopsy Ishak Score	FibroScan (kPa)	FibroTest*
F0 – F1	0 or 1	0, 1, or 2	< 8.8	≤ 0.48
F2	2	3	≥ 8.8 to < 9.6	0.49 to 0.58
F3	3	4	≥ 9.6 to < 12.5	0.59 to 0.72
F4	4	≥ 5	≥ 12, 5	≥ 0.73

* APRI will not be used to derive Baseline Fibrosis Stage. However, per inclusion/exclusion criteria, subjects need to have concordant FibroTest and APRI scores in order to determine eligibility.

Presence or absence of cirrhosis will be determined as collected in EDC ("What is the subject's cirrhosis status?" – "cirrhotic" or "non-cirrhotic").

Baseline Child-Pugh score is the sum of the points assigned for each of the five observed findings as defined in [Table 12](#).

Table 12. Child-Pugh Classification of Severity of Cirrhosis

Parameter	Points Assigned for Observed Findings		
	1	2	3
Total bilirubin, µmol/L (mg/dL)	< 34.2 (< 2)	34.2 – 51.3 (2 – 3)	> 51.3 (> 3)
Serum albumin, g/L (g/dL)	> 35 (> 3.5)	28 – 35 (2.8 – 3.5)	< 28 (< 2.8)
INR	< 1.7	1.7 – 2.3	> 2.3
Ascites*	None	Slight	Moderate to severe
Hepatic encephalopathy**	None	Grade 1 or 2 (or suppressed with medication)	Grade 3 or 4 (or refractory)

* None.

Slight ascites = Ascites detectable only by ultrasound examination.

Moderate ascites = Ascites manifested by moderate symmetrical distension of the abdomen.

Severe ascites = Large or gross ascites with marked abdominal distension.

** None: normal consciousness, personality, neurological examination, electroencephalogram.

Grade 1: restless, sleep disturbed, irritable/agitated, tremor, impaired handwriting, 5 cps waves.

Grade 2: lethargic, time-disoriented, inappropriate behavior, asterixis, ataxia, slow triphasic waves.

Grade 3: somnolent, stuporous, place-disoriented, hyperactive reflexes, rigidity, slower waves.

Grade 4: unarousable coma, no personality/behavior, decerebrate, slow 2 to 3 cps delta activity.

Baseline APRI and FIB-4 are defined as the equations below. Subjects who do not have concurrent AST and platelet values at baseline will be excluded from the summary of baseline APRI. Age is defined in years at baseline. Subjects who do not have concurrent values of AST, ALT, and platelet count at baseline, or subjects who are missing age will be excluded from the summary of FIB-4.

$$\text{APRI} = \frac{\frac{\text{AST Level (U/L)}}{\text{AST (Upper Limit of Normal)(U/L)}}}{\text{Platelet Count (10}^9\text{/L)}} \times 100$$

$$\text{FIB-4} = \frac{\text{Age (years)} \times \text{AST Level (U/L)}}{\text{Platelet Count (10}^9\text{/L)} \times \sqrt{\text{ALT (U/L)}}}$$

Histories of bleeding disorders and depression or bipolar disorder will be based on the Medical History (MH) eCRF, as defined in [Table 13](#).

Table 13. Medical/Surgical History eCRF

Subgroup	Medical History eCRF	
	Body System	Condition/Diagnosis
Bleeding disorders	Blood	Clotting/bleeding problems Factor deficiency Hemophilia Von Willebrand disease
Depression or bipolar disorder	Neurologic and Psychiatric System	Bipolar disorder Depression

